11. ADVERSE EVENTS

The study Investigator and Coordinator will evaluate, characterize and record in the CRF all adverse events (AEs) occurring in all subjects from the initiation of study treatment to study exit (or premature withdrawal). Device or procedure related AEs will be followed until resolution. AEs may be reported spontaneously by the subject or detected by the Investigator or coordinator. AEs should be evaluated for diagnoses not just symptoms (i.e., “angina”, not “chest pain”).

AEs may be either spontaneously reported or elicited during questioning and examination of a subject. All AEs must be completely recorded within the Subject's source documentation. All AEs will be evaluated by the Investigator for relationship to the iovera[°] device and to the treatment.

In addition to verbatim terms, the Sponsor will categorize all AEs using MedDRA preferred terms and system organ classes (SOC). Analysis will report both verbatim and MedDRA terms.

Adverse events¹ (AEs) will be assessed continuously from the initiation of study treatment through study exit. Per ISO14155:2011, an AE is any untoward medical occurrence, unintended disease or injury, or untoward clinical signs in subjects, users or other persons, whether or not related to the investigational medical device. An AE can arise from any use of the device (e.g., off-label use, use in combination with any drug) and from any route of administration.

Timely and complete reporting of all AEs assists the Sponsor in identifying any untoward medical occurrence, thereby allowing:

- 1) protection of the safety of study subjects;
- 2) a greater understanding of the overall safety profile of the device;
- 3) recognition of device-related ill effects;
- 4) appropriate modification of study protocols;
- 5) improvements in study design or procedures; and
- 6) adherence to worldwide regulatory requirements.

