## **9.0 SAFETY ANALYSES**

All adverse event analyses will be performed on the Safety Population.

The summary of AEs will be limited to treatment emergent AEs. For AEs with a missing start date, the AE will be considered treatment emergent unless there is additional information indicating that the AE started prior to study treatment.

Adverse events (AEs) will be coded using the Medical Dictionary for Regulatory Activities (MedDRA). Treatment-emergent AEs (TEAEs) are defined as any adverse event with onset on or after study treatment begins or any adverse event already present at baseline that worsens in severity. For AEs with missing start dates, the AE will be considered treatment-emergent unless there is additional information indicating that the AE started prior to study treatment. Only treatment emergent AEs will be summarized.

The number and percentage of subjects with at least one TEAE, at least one iovera procedure-related TEAE, at least one iovera device-related TEAE, at least one opioid use related TEAE, at least one serious TEAE, and at least one TEAE leading to study withdrawal will be presented by treatment group. AEs that are definitely, probably, or possibly related, or for which the relationship is missing, will be considered related.

The number and percentage of subjects having a TEAE in each System Organ Class (SOC) and having each individual type of adverse event (Preferred Term) will be presented. TEAEs will also be summarized at the event level by SOC/Preferred Term and severity. This will be done for all TEAEs, iovera procedure related TEAEs, iovera device related TEAEs, and opioid use related TEAEs.

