		95% CI for Mean (1)	(xx.x, xx.x)	(xx.x, xx.x)	
	72 Hours Post-op to 2 Weeks Post-op	n	xx	xx	
		Mean	xx.x	xx.x	xx.x (xx.x, xx.x)
		Median	xx.x	xx.x	
		SD	xx.x	xx.x	
		Minimum - Maximum	xx - xx	xx - xx	
		95% CI for Mean (1)	(xx.x, xx.x)	(xx.x, xx.x)	
	2 Weeks Post-op to 6 Weeks Post-op	...	...	...	...
	6 Weeks Post-op to 12 Weeks Post-op	...	...	...	...
	Hospital Discharge to 2 Weeks Post-op	n	xx	xx	
		Mean	xx.x	xx.x	xx.x (xx.x, xx.x)
		Median	xx.x	xx.x	
		SD	xx.x	xx.x	
		Minimum - Maximum	xx - xx	xx - xx	
		95% CI for Mean (1)	(xx.x, xx.x)	(xx.x, xx.x)	
	Hospital Discharge to 6 Weeks Post-op	p-value (2)			x.xxxx
		...	...	...	...
		...	...	...	...

Program Name:

Creation date, time

Source: Listing 4

Note: Missing pill count data were imputed using multiple imputation methods.

(1) Confidence interval based on the t-distribution.

(2) p-value from a one-sided, two sample t-test, testing the null hypothesis that the true iovera mean is greater than or equal to the true Standard of Care mean versus the alternative hypothesis that the true iovera mean is less than the true Standard of Care mean.

Table 6.1 will be repeated in the following tables:

Table 6.2

OPIOID CONSUMPTION: TOTAL DAILY MORPHINE EQUIVALENT (TME):  
EXCLUDES DISCONTINUATIONS DUE TO ADVERSE EVENTS  
ITT POPULATION

Table 7.1

OPIOID CONSUMPTION: TOTAL DAILY MORPHINE EQUIVALENT (TME)  
PER PROTOCOL POPULATION

Table 7.2

OPIOID CONSUMPTION: TOTAL DAILY MORPHINE EQUIVALENT (TME):  
EXCLUDES DISCONTINUATIONS DUE TO ADVERSE EVENTS  
PER PROTOCOL POPULATION

*Programming note: for Tables 6.2 and 7.2, please add Listing 2.1 to Source.*

Table 8.1

TREATMENT EMERGENT ADVERSE EVENTS (TEAEs): OVERVIEW (SUBJECT LEVEL)  
SAFETY POPULATION

Parameter	OCS (N=xx) n (%)	Standard of Care (N=xx) n (%)
At least one TEAE	xx (xx.x)	xx (xx.x)
At least one iovera procedure-related TEAE (1)	xx (xx.x)	-
At least one iovera device-related TEAE (1)	xx (xx.x)	-
At least one opioid use related TEAE (1)	xx (xx.x)	xx (xx.x)
At least one serious TEAE	xx (xx.x)	xx (xx.x)
At least one TEAE leading to study withdrawal	xx (xx.x)	xx (xx.x)

Program Name:

Creation date, time:

Source: Listing 2.1

Note: Percentages are calculated based on the number of subjects in the ITT Population.

(1) Adverse events that are definitely, probably, or possibly related, or for which the relationship is missing, are considered related.

Table 8.2

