Note: The denominator for the calculation of the percentage is the number of AEs with non-missing severity with the given preferred term or in the given system organ class. Adverse events that are definitely, probably, or possibly related, or for which the relationship is missing, are considered related.

Table 9.5

OPIOID USE RELATED TREATMENT EMERGENT ADVERSE EVENTS: INCIDENCE BY SYSTEM ORGAN CLASS AND PREFERRED TERM (SUBJECT LEVEL)  
SAFETY POPULATION

System Organ Class/Preferred Term	Iovera (N=xx) n (%)	Standard of Care (N=xx) n (%)
System Organ Class 1	xx (xx.x)	xx (xx.x)
Preferred Term 1	xx (xx.x)	xx (xx.x)
Preferred Term 2	xx (xx.x)	xx (xx.x)
...		
System Organ Class 2	xx (xx.x)	xx (xx.x)
Preferred Term 1	xx (xx.x)	xx (xx.x)
Preferred Term 2	xx (xx.x)	xx (xx.x)
...		

Program Name: Creation date, time

Source: Listing 2.1

Note: The denominator for the calculation of the percentage is N, the number of subjects in the treatment group, and the numerator is the number of subjects with at least one AE in that system organ class or with that preferred term. Adverse events that are definitely, probably, or possibly related, or for which the relationship is missing, are considered related.

Table 9.6

OPIOID USE RELATED TREATMENT EMERGENT ADVERSE EVENTS BY SYSTEM ORGAN CLASS/PREFERRED TERM AND SEVERITY (EVENT LEVEL)  
SAFETY POPULATION

Iovera (N=xx)

System Organ Class/Preferred Term	Mild	Moderate	Severe	Total with Non-Missing Severity	
	n (%)	n (%)	n (%)	n (100%)	n
Any Adverse Event	xx (xx.x)	xx (xx.x)	xx (xx.x)	xx (100.0)	xx
System Organ Class 1	xx (xx.x)	xx (xx.x)	xx (xx.x)	xx (100.0)	xx
Preferred Term 1	xx (xx.x)	xx (xx.x)	xx (xx.x)	xx (100.0)	xx
Preferred Term 2	xx (xx.x)	xx (xx.x)	xx (xx.x)	xx (100.0)	xx
...					

Program Name:

Creation date, time

Source: Listing 2.1

Note: The denominator for the calculation of the percentage is the number of AEs with non-missing severity with the given preferred term or in the given system organ class. Adverse events that are definitely, probably, or possibly related, or for which the relationship is missing, are considered related.

[Note: This table will be continued for Standard of Care.]

[figure not shown]

Table 11

SUBJECT SATISFACTION  
ITT POPULATION

[figure not shown]
Visit	Variable	Statistic	Iovera (N=xx)	Standard of Care (N=xx)
Week 6	Overall knee pain status since the beginning of the study			
	Very much worse	n (%)	xx (xx.x)	xx (xx.x)
	Much worse	n (%)	xx (xx.x)	xx (xx.x)

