**Listing 2.1**

**ADVERSE EVENTS (AEs)**

**SAFETY POPULATION**

**Part 3 of 3**

Treatment Group	Subject Number	Event	Relatedness			If 'Possible', 'Probable', or 'Definite' in #1, Pre-Existing Condition
			To Iovera Procedure	To Iovera Device	To Pre-Existing Condition (#1)	
xxxxxxxxx	xxx	xxxxxx	xxxxxxxx	xxxxxxxxx	xxxxxxxx	xxxxxxxxxxxx

---

Program Name:

Creation date, time

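### The opioid-related TEAE tables cannot be derived from their stated source listing, and the SAP counts any event without an opioid rating as opioid-related

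*SAP*

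**What the plan says.** SAP section 9.0 lists, among the subject-level safety summaries by treatment group, "at least one opioid use related TEAE". It also plans breakdowns of these events by system organ class, preferred term and severity. The same section gives a single classification rule, not restricted to any type of relationship: "AEs that are definitely, probably, or possibly related, or for which the relationship is missing, will be considered related".

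The shells follow the text. Table 8.1 has an opioid row for both arms, footnoted with the rule. Tables 9.5 (subject level) and 9.6 (event level) repeat it underneath: "Adverse events that are definitely, probably, or possibly related, or for which the relationship is missing, are considered related". All three carry the line "Source: Listing 2.1".

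Part 3 of Listing 2.1 has three relatedness ratings: iovera procedure, iovera device and, last, "To Pre-Existing Condition (#1".

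On what is rated, protocol section 11 says: "All AEs will be evaluated by the Investigator for relationship to the iovera[°] device and to the treatment". The five-grade scale in protocol Table 4 (section 11.3) is headed for the study device or procedure. Protocol section 10.4.4 has its own rule for missing relatedness, which makes an event device-related when the device rating is missing. That section plans no opioid-related summary. Protocol section 9.6 says that data taken from hospital records may include opioid-related adverse events, without giving a grade, a definition or a method after discharge.

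**The concern.** A table of opioid-related events needs a variable saying which events are opioid-related. Neither document says who makes that judgement, on what scale or over what period, and the named source does not display it. The rule for missing values then decides how unrated events are classified.

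For a device rating, counting blanks as related is a familiar cautious choice, because it avoids understating harm from the product under study. That reasoning does not carry over to opioid relatedness. There, blanks bring in events of any cause, including complications of the operation.

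The background sections of both documents give fewer opioid side effects as a reason for reducing opioid use. Tables 8.1, 9.5 and 9.6 are where the trial would show whether this happened. If they contain unrated events, they do not answer that question.

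**Working it through.** The documents give no figure to reproduce. The check is a trace from text to table to listing to protocol.

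1. **Text to tables.** SAP 9.0 plans opioid-related TEAEs; Tables 8.1, 9.5 and 9.6 deliver them. The rule that missing means related is attached to the opioid row of Table 8.1 and to both other tables.

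2. **Tables to source.** All three name Listing 2.1.
   - Part 1 holds the event, its description, coding, start date and window.
   - Part 2 holds severity, seriousness, action taken and study exit.
   - Part 3 holds the three relatedness ratings and the name of any pre-existing condition.
   - No part has an opioid field, nor does Listing 2.2.
   - In Part 3 the seven headings match seven placeholder cells and no redaction is marked, so a column lost from the text is unlikely.

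3. **Source to protocol.** The protocol's rating instruction covers device and treatment, its scale covers device or procedure, and its rule for missing ratings covers the device. The SAP extends that rule to opioid relatedness. SAP section 3.5, on changes to protocol-specified analyses, describes only a change to the multiple imputation analysis.

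4. **Effect of the rule.** Let R be the TEAEs rated definite, probable or possible for opioid relatedness, and M those with no rating. The SAP reports R + M. The overcount is the part of M that is not opioid-related, so it lies between zero and M. The documents do not give M. Three readings are possible:
   - *Rating collected but left off the listing shell.* The tables can be produced but not traced to Listing 2.1, and every blank is still counted as opioid-related.
   - *Rating not collected, and its absence not coded as missing.* Tables 9.5 and 9.6 cannot be produced from Listing 2.1.
   - *Rating not collected, and its absence coded as missing.* R = 0 and M is all TEAEs, so R + M is all TEAEs. Table 9.5 duplicates Table 8.2, Table 9.6 duplicates Table 8.3, and the opioid row of Table 8.1 equals its any-TEAE row in each arm.

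5. **Balance between arms.** Adverse events are recorded from the start of study treatment (protocol section 11). The iovera visit is 5 ± 2 days before surgery (section 9.5), that is 5 − 2 = 3 to 5 + 2 = 7 days before. Protocol section 8.4 lists bruising, swelling and altered sensation among the known risks of the procedure. Such events can precede the operation and the post-operative opioids, and they arise from a procedure that only one arm receives. Left unrated for opioids, they enter the opioid-related count of the iovera arm, with no counterpart under standard of care.

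**The case against.** A reader might infer that, as the SAP stands, every TEAE becomes opioid-related. The documents do not support that. A listing shell is an output layout, not the case report form or the dataset, and the form is not in the documents. Wording about definite, probable or possible relatedness with some values missing fits a graded rating that is occasionally blank at least as well as one never collected. Protocol section 9.6 also foresees that opioid-related events may be picked up from hospital records. The all-events result needs two assumptions: that no rating was collected, and that its absence is coded as missing.

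The other side can also say that the rule applies equally to both arms and errs towards reporting harm. SAP section 4.4 names all TEAEs as the only safety endpoint, the opioid tables involve no test, and Tables 8.2 and 8.3 still show every preferred term by arm.

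All of this limits the importance of the point but does not remove it. Section 9.6 gives no scale and nothing after discharge. A rule that is the same in both arms does not act equally when one arm has an extra procedure with its own local effects. In an unblinded trial (SAP section 3.3), the frequency of blank ratings may also differ by arm. Under each of the three readings, the opioid tables either cannot be traced to their source, cannot be produced from it, or repeat the all-event tables.

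**Conclusion.** The point holds as a fault of definition and traceability, together with a misapplied rule for missing ratings. That Listing 2.1 has no opioid rating, that the three tables name it as source, and that blanks count as opioid-related can all be read directly from the SAP. Full duplication of Tables 8.2 and 8.3 by Tables 9.5 and 9.6 is only the extreme case and rests on the two assumptions above.

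No numerical size can be given, because the documents do not state how many events lack an opioid rating. The consequence is confined to descriptive safety tables; the primary test on opioid consumption and the key secondary KOOS JR. test are unaffected. It is worth correcting before the safety tables are run, because those tables bear on a stated reason for reducing opioid use.

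**What to change.** In SAP section 9.0 and the footnotes to Tables 8.1, 9.5 and 9.6, limit the rule that missing means related to the iovera device and iovera procedure ratings. Then define opioid relatedness in one of two ways:

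- **If a rating is collected:** state who makes it, on what scale and over what period. Add it as a column in Listing 2.1, count definite, probable or possible as related, and report missing ratings as a separate row by arm. Separate reporting avoids treating blanks silently as either related or unrelated.
- **If no rating is collected:** use a list of MedDRA preferred terms, fixed without reference to treatment arm and applied identically to both arms.

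Note the extension beyond the protocol's device-only rule in SAP section 3.5.

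The cost is a revised sentence with matching footnotes, a definition or term list, and, if a rating exists, one listing column and one table row. The drawback of a term list is that it drops the causality judgement and will include some events with other causes; the table footnote should say so.

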## **10.0 OTHER ANALYSES**

Study exit data consist of the primary reason that the subject is off study and adverse event status at study exit (whether or not there were any unresolved adverse events). End of study data will be summarized by treatment group using counts and percentages.

Protocol deviations will be summarized by type of deviation and overall using counts and percentages.

These analyses will be performed for the ITT Population.

## Appendix 1:

# KOOS, JR SCORING INSTRUCTIONS

The KOOS, JR was developed from the original long version of the Knee injury and Osteoarthritis Outcome Score (KOOS) survey using Rasch analysis. The KOOS, JR contains 7 items from the original KOOS survey. Items are coded from 0 to 4, none to extreme respectively.

KOOS, JR is scored by summing the raw response (range 0-28) and then converting it to an interval score using the table provided below. The interval score ranges from 0 to 100 where 0 represents total knee disability and 100 represents perfect knee health.

Table for converting raw summed scores to interval level scores from 0 (total knee disability) to 100 (perfect knee health)

Raw summed score (0-28)	Interval score (0 to 100 scale)
0	100.000
1	91.975
2	84.600
3	79.914
4	76.332
5	73.342
6	70.704
7	68.284
8	65.994
9	63.776
10	61.583
11	59.381
12	57.140
13	54.840
14	52.465
15	50.012
16	47.487
17	44.905
18	42.281
19	39.625
20	36.931
21	34.174
22	31.307
23	28.251
24	24.875
25	20.941
26	15.939
27	8.291
28	0.000

## Appendix 2: Opioid Morphine Equivalent Conversion Factors

Type of Opioid	MME Conversion Factor
Buprenorphine patch 	12.6
Buprenorphine tab or film	10
Butorphanol	7
Codeine	0.15
Dihydrocodeine	0.25
Fentanyl buccal or SL tablets, or lozenge/troche 	0.13
Fentanyl film or oral spray 	0.18
Fentanyl nasal spray 	0.16
Fentanyl patch 	7.2
Hydrocodone	1
Hydromorphone	4
Levorphanol tartrate	11
Meperidine hydrochloride	0.1
Methadone	3
Morphine	1
Nalbuphine	1
Opium	1
Oxycodone	1.5
Oxymorphone	3
Pentazocine	0.37
Tapentadol	0.4
Tramadol	0.1

Centers for Disease Control and Prevention, Atlanta, GA, May 2014. For more information, send an email to [contact].

The MME conversion factor for buprenorphine patches is based on the assumption that one milligram of parenteral buprenorphine is equivalent to 75 milligrams of oral morphine and that one patch delivers the dispensed micrograms per hour over a 24 hour day. Example: 5 ug/hr buprenorphine patch \* 24 hrs = 120 ug/day buprenorphine = 0.12 mg/day buprenorphine = 9 mg/day oral morphine milligram equivalent. In other words, the conversion factor not accounting for days of use would be 9/5 or 1.8. However, since the buprenorphine patch remains in place for 7 days, we have multiplied the conversion factor by 7 (1.8 X 7 = 12.6). In this example, MME/day for four 5  $\mu$ g/hr buprenorphine patches dispensed for use over 28 days would work out as follows: Example: 5 ug/hr buprenorphine patch \* (4 patches/28 days)\* 12.6 = 9 MME/day.

The MME conversion factor for fentanyl buccal tablets, sublingual tablets, and lozenges/troche is 0.13. This conversion factor should be multiplied by the number of micrograms in a given lozenge/troche.

The MME conversion factor for fentanyl film and oral spray is 0.18. This reflects a 40% greater bioavailability for films compared to lozenges/tablets and 38% greater bioavailability for oral sprays compared to lozenges/tablets.

The MME conversion factor for fentanyl nasal spray is 0.16, which reflects a 20% greater bioavailability for sprays compared to lozenges/tablets.

The MME conversion factor for fentanyl patches is based on the assumption that one milligram of parenteral fentanyl is equivalent to 100 milligrams of oral morphine and that one patch delivers the dispensed micrograms per hour over a 24 hour day. Example: 25 ug/hr fentanyl patch \* 24 hrs = 600 ug/day fentanyl = 60 mg/day oral morphine milligram equivalent. In other words, the conversion factor not accounting for days of use would be 60/25 or 2.4. However, since the fentanyl patch remains in place for 3 days, we have multiplied the conversion

factor by 3 ( $2.4 \times 3 = 7.2$ ). In this example, MME/day for ten 25  $\mu$ g/hr fentanyl patches dispensed for use over 30 days would work out as follows: Example: 25  $\mu$ g/hr fentanyl patch \* (10 patches/30 days)\* 7.2 = 60 MME/day.

## Appendix A: TABLE SHELLS

## Appendix B: LISTING SHELLS

Table 1.1

DEMOGRAPHICS  
ITT POPULATION

Variable	Statistic	Iovera (N=xx)	Standard of Care (N=xx)	Total (N=xxx)
Age (years) (1)	n	xx	xx	xx
	Mean	xx.xx	xx.xx	xx.xx
	Median	xx.xx	xx.xx	xx.xx
	SD	xx.xx	xx.xx	xx.xx
	Minimum - Maximum	xx.x - xx.x	xx.x - xx.x	xx.x - xx.x
Gender				
Female	n (%)	xx (xx.x)	xx (xx.x)	xxx (xx.x)
Male	n (%)	xx (xx.x)	xx (xx.x)	xxx (xx.x)
Ethnicity				
Hispanic or Latino	n (%)	xx (xx.x)	xx (xx.x)	xxx (xx.x)
Not Hispanic or Latino	n (%)	xx (xx.x)	xx (xx.x)	xxx (xx.x)
Race (2)				
White	n (%)	xx (xx.x)	xx (xx.x)	xxx (xx.x)
Black or African American	n (%)	xx (xx.x)	xx (xx.x)	xxx (xx.x)
Asian	n (%)	xx (xx.x)	xx (xx.x)	xxx (xx.x)
American Indian or Alaska Native	n (%)	xx (xx.x)	xx (xx.x)	xxx (xx.x)
Native Hawaiian or Other Pacific Islander	n (%)	xx (xx.x)	xx (xx.x)	xxx (xx.x)
Other	n (%)	xx (xx.x)	xx (xx.x)	xxx (xx.x)
Missing	n	xx	xx	xxx

Program Name:

Creation date, time

(1) Age = (Date of informed consent - date of birth)/365.25.

(2) Subjects may check more than one race category, so the percentages may sum to more than 100%.

[Note: This table will be repeated for the Per Protocol Population (Table 1.2).]

Table 2

NUMERIC RATING SCALE (NRS) FOR PAIN  
ITT POPULATION

Parameter	Visit	Statistic	Iovera (N=xx)		Standard of Care (N=xx)		Difference in Mean Change from Baseline (Iovera - Standard of Care) and 95% CI (1)
			Value	Change from Baseline	Value	Change from Baseline	
Pain in the past 7 days	Screening (Baseline)	n	xx		xx		
		Mean	x.x		x.x		
		Median	x.x		x.x		
		SD	x.x		x.x		
		Minimum - Maximum	x - x		x - x		
	72 Hours Post-op	95% CI for Mean (1)	(x.x, x.x)		(x.x, x.x)		
		n	xx	xx	xx	xx	
		Mean	x.x	x.x	x.x	x.x	x.x (x.x, x.x)
		Median	x.x	x.x	x.x	x.x	
		SD	x.x	x.x	x.x	x.x	
	2 Weeks Post-op	Minimum - Maximum	x - x	x - x	x - x	x - x	
		95% CI for Mean (1)	(x.x, x.x)	(x.x, x.x)	(x.x, x.x)	(x.x, x.x)	
		p-value (2)					x.xxxx
		2 Weeks Post-op	...	...	...	...	...
		6 Weeks Post-op	...	...	...	...	...
AUC/time for Change from Baseline in Pain in the past 7 days	Baseline through 72 Hours Post-op	n	xx		xx		
		Mean	xx.xx		xx.xx		x.x (x.x, x.x)
		Median	xx.xx		xx.xx		
		SD	xx.xx		xx.xx		
		Minimum - Maximum	xx.x - xx.x		xx.x - xx.x		
	12 Weeks Post-op	95% CI for Mean (1)	(xx.xx, xx.xx)		(xx.xx, xx.xx)		
		p-value (3)	x.xxxx		x.xxxx		
		p-value (4)					x.xxxx
		2 Weeks Post-op	...	...	...	...	...
		6 Weeks Post-op	...	...	...	...	...
	Baseline through	...	...	...	...	...	...

---

12 Weeks Post-op

Program Name:

Creation date, time

Note: Change from baseline = Baseline value - post-baseline value, so that a positive change value indicates pain relief.

NRS values range from 0 (no pain) to 10 (worst pain imaginable).

(1) Confidence interval based on the t-distribution.

(2) p-value from a two-sided, two-sample t-test, testing the null hypothesis that the iovera and Standard of Care means are equal versus the alternative hypothesis that they are unequal.

(3) p-value from a two-sided, paired t-test, testing the null hypothesis that the true mean equals 0.

(4) p-value from a one-sided, two-sample t-test, testing the null hypothesis that the iovera mean is less than or equal to the Standard of Care mean versus the alternative hypothesis that the iovera mean is greater than the Standard of Care mean.

Table 2 (continued)

NUMERIC RATING SCALE (NRS) FOR PAIN  
ITT POPULATION

Parameter	Visit	Statistic	Iovera (N=xx)		Standard of Care (N=xx)		Difference in Mean Change from Baseline (Iovera - Standard of Care) and 95% CI (1)
			Value	Change from Baseline	Value	Change from Baseline	
Pain right now	Screening (Baseline)	n	xx		xx		
		Mean	x.x		x.x		
		Median	x.x		x.x		
		SD	x.x		x.x		
		Minimum - Maximum	x - x		x - x		
	72 Hours Post-op	95% CI for Mean (1)	(x.x, x.x)		(x.x, x.x)		
		n	xx	xx	xx	xx	
		Mean	x.x	x.x	x.x	x.x	x.x (x.x, x.x)
		Median	x.x	x.x	x.x	x.x	
		SD	x.x	x.x	x.x	x.x	
	2 Weeks Post-op 6 Weeks Post-op 12 Weeks Post-op	Minimum - Maximum	x - x	x - x	x - x	x - x	
		95% CI for Mean (1)	(x.x, x.x)	(x.x, x.x)	(x.x, x.x)	(x.x, x.x)	
		p-value (2)					x.XXXX
AUC/time for Change from Baseline in Pain right now	Baseline through 72 Hours Post-op	n	xx		xx		
		Mean	xx.xx		xx.xx		x.x (x.x, x.x)
		Median	xx.xx		xx.xx		
		SD	xx.xx		xx.xx		
		Minimum - Maximum	xx.x - xx.x		xx.x - xx.x		
	Baseline through 2 Weeks Post-op Baseline through 6 Weeks Post-op Baseline through 12 Weeks Post-op	95% CI for Mean (1)	(xx.xx, xx.xx)		(xx.xx, xx.xx)		
		p-value (3)	x.XXXX		x.XXXX		
		p-value (4)					x.XXXX

---

Program Name:

Creation date, time

Note: Change from baseline = Baseline value - post-baseline value, so that a positive change value indicates pain relief.  
NRS values range from 0 (no pain) to 10 (worst pain imaginable).

(1) Confidence interval based on the t-distribution.

(2) p-value from a two-sided, two-sample t-test, testing the null hypothesis that the iovera and Standard of Care means are equal versus the alternative hypothesis that they are unequal.

(3) p-value from a two-sided, paired t-test, testing the null hypothesis that the true mean equals 0.

(4) p-value from a one-sided, two-sample t-test, testing the null hypothesis that the iovera mean is less than or equal to the Standard of Care mean versus the alternative hypothesis that the iovera mean is greater than the Standard of Care mean.

Table 3

KOOS JR.  
ITT POPULATION

Parameter	Visit	Statistic	Iovera (N=xx)		Standard of Care (N=xx)		Difference in Mean Change from Baseline (Iovera - Standard of Care) and 95% CI (1)
			Value	Change from Baseline	Value	Change from Baseline	
Overall Score	Screening (Baseline)	n	xx		xx		
		Mean	xx.x		xx.x		
		Median	xx.x		xx.x		
		SD	xx.x		xx.x		
		Minimum - Maximum	xx - xx		xx - xx		
	72 Hours Post-op	95% CI for Mean (1)	(xx.x, xx.x)		(xx.x, xx.x)		
		n	xx	xx	xx	xx	
		Mean	xx.x	xx.x	xx.x	xx.x	xx.x (xx.x, xx.x)
		Median	xx.x	xx.x	xx.x	xx.x	
		SD	xx.x	xx.x	xx.x	xx.x	
	2 Weeks Post-op 6 Weeks Post-op 12 Weeks Post-op	Minimum - Maximum	xx - xx	xx - xx	xx - xx	xx - xx	
		95% CI for Mean (1)	(xx.x, xx.x)	(xx.x, xx.x)	(xx.x, xx.x)	(xx.x, xx.x)	
		...	...	...	...	...	...
		...	...	...	...	...	...
		...	...	...	...	...	...
AUC/time for Change from Baseline in Overall Score	Baseline through 72 Hours Post-op	n	xx		xx		
		Mean	xx.xx		xx.xx		xx (x.x, x.x)
		Median	xx.xx		xx.xx		
		SD	xx.xx		xx.xx		
		Minimum - Maximum	xx.x - xx.x		xx.x - xx.x		
	Baseline through 2 Weeks Post-op 6 Weeks Post-op 12 Weeks Post-op	95% CI for Mean (1)	(xx.xx, xx.xx)		(xx.xx, xx.xx)		
		p-value (2)	x.xxxx		x.xxxx		
		p-value (3)				x.xxxx	
		...	...	...	...	...	...
		...	...	...	...	...	...

Program Name:

Creation date, time

Note: Change from baseline = Post-baseline value - Baseline value, so that a positive change value indicates a positive outcome. Missing overall scores were imputed using multiple imputation methods.

Koos JR. normalized scores range from 0 (extreme symptoms) to 100 (no symptoms).

(1) Confidence interval based on the t-distribution.

(2) p-value from a two-sided, paired t-test, testing the null hypothesis that the true mean equals 0.

(3) p-value from a one-sided, two-sample t-test, testing the null hypothesis that the Standard of Care mean minus the iovera mean is greater than or equal to the non-inferiority margin of 14 versus the alternative hypothesis that the difference in means is less than 14.

[figure not shown]

Table 5

TIMED GET UP AND GO (TUG) TEST  
ITT POPULATION

Parameter	Visit	Statistic	Iovera (N=xx)	Standard of Care (N=xx)		Difference in Mean Change from Baseline (Iovera - Standard of Care) and 95% CI (1)
			Value	Change from Baseline	Value	
TUG Time (seconds)	Screening (Baseline)	n (% of subjects)	xx (xx.x)		xx (xx.x)	
		Mean	xx.x		xx.x	
		Median	xx.x		xx.x	
		SD	xx.x		xx.x	
		Minimum - Maximum	xx - xx		xx - xx	
	2 Weeks Post-op	95% CI for Mean (1)	(xx.x, xx.x)		(xx.x, xx.x)	
		n (% of subjects)	xx (xx.x)	xx	xx (xx.x)	xx
		Mean	xx.x	xx.x	xx.x	xx.x
		Median	xx.x	xx.x	xx.x	xx.x
		SD	xx.x	xx.x	xx.x	xx.x
	6 Weeks Post-op 12 Weeks Post-op	Minimum - Maximum	xx - xx	xx - xx	xx - xx	xx - xx
		95% CI for Mean (1)	(xx.x, xx.x)	(xx.x, xx.x)	(xx.x, xx.x)	(xx.x, xx.x)
		...	...	...	...	...
		...	...	...	...	...
		...	...	...	...	...
AUC/time for Change from Baseline in TUG time	Baseline through 2 Weeks Post-op	n	xx		xx	
		Mean	xx.xx		xx.xx	x.x (x.x, x.x)
		Median	xx.xx		xx.xx	
		SD	xx.xx		xx.xx	
		Minimum - Maximum	xx.x - xx.x		xx.x - xx.x	
	6 Weeks Post-op 12 Weeks Post-op	95% CI for Mean (1)	(xx.xx, xx.xx)		(xx.xx, xx.xx)	
		p-value (2)	x.XXXX		x.XXXX	
		p-value (3)				x.XXXX
		...	...	...	...	...
		...	...	...	...	...

Program Name:

Creation date, time

Note: Change from baseline = Baseline value - post-baseline value, so that a positive change value indicates a positive outcome.

(1) Confidence interval based on the t-distribution.

(2) p-value from a two-sided, paired t-test, testing the null hypothesis that the true mean equals 0.

(3) p-value from a one-sided, two-sample t-test, testing the null hypothesis that the iovera mean is less than or equal to the Standard of Care mean versus the alternative hypothesis that the iovera mean is greater than the Standard of Care mean.

Table 6.1

OPIOID CONSUMPTION: TOTAL DAILY MORPHINE EQUIVALENT (TME)  
ITT POPULATION

Parameter	Time Period	Statistic	Iovera (N=xx)	Standard of Care (N=xx)	Difference between Treatments (Standard of Care - Iovera) and 95% CI (1)
TME	TKA to 72 Hours Post-op	n	xx	xx	
		Mean	xx.x	xx.x	xx.x (xx.x, xx.x)
		Median	xx.x	xx.x	
		SD	xx.x	xx.x	
		Minimum - Maximum	xx - xx	xx - xx	
		95% CI for Mean (1)	(xx.x, xx.x)	(xx.x, xx.x)	
	72 Hours Post-op to 2 Weeks Post-op	n	xx	xx	
		Mean	xx.x	xx.x	xx.x (xx.x, xx.x)
		Median	xx.x	xx.x	
		SD	xx.x	xx.x	
		Minimum - Maximum	xx - xx	xx - xx	
		95% CI for Mean (1)	(xx.x, xx.x)	(xx.x, xx.x)	
	2 Weeks Post-op to 6 Weeks Post-op	...	...	...	...
	6 Weeks Post-op to 12 Weeks Post-op	...	...	...	...
	Hospital Discharge to 2 Weeks Post-op	n	xx	xx	
		Mean	xx.x	xx.x	xx.x (xx.x, xx.x)
		Median	xx.x	xx.x	
		SD	xx.x	xx.x	
		Minimum - Maximum	xx - xx	xx - xx	
		95% CI for Mean (1)	(xx.x, xx.x)	(xx.x, xx.x)	
	Hospital Discharge to 6 Weeks Post-op	p-value (2)			x.xxxx
		...	...	...	...
		...	...	...	...

Program Name:

Creation date, time

Source: Listing 4

Note: Missing pill count data were imputed using multiple imputation methods.

(1) Confidence interval based on the t-distribution.

(2) p-value from a one-sided, two sample t-test, testing the null hypothesis that the true iovera mean is greater than or equal to the true Standard of Care mean versus the alternative hypothesis that the true iovera mean is less than the true Standard of Care mean.

Table 6.1 will be repeated in the following tables:

Table 6.2

OPIOID CONSUMPTION: TOTAL DAILY MORPHINE EQUIVALENT (TME):  
EXCLUDES DISCONTINUATIONS DUE TO ADVERSE EVENTS  
ITT POPULATION

Table 7.1

OPIOID CONSUMPTION: TOTAL DAILY MORPHINE EQUIVALENT (TME)  
PER PROTOCOL POPULATION

Table 7.2

OPIOID CONSUMPTION: TOTAL DAILY MORPHINE EQUIVALENT (TME):  
EXCLUDES DISCONTINUATIONS DUE TO ADVERSE EVENTS  
PER PROTOCOL POPULATION

*Programming note: for Tables 6.2 and 7.2, please add Listing 2.1 to Source.*

Table 8.1

TREATMENT EMERGENT ADVERSE EVENTS (TEAEs): OVERVIEW (SUBJECT LEVEL)  
SAFETY POPULATION

Parameter	OCS (N=xx) n (%)	Standard of Care (N=xx) n (%)
At least one TEAE	xx (xx.x)	xx (xx.x)
At least one iovera procedure-related TEAE (1)	xx (xx.x)	-
At least one iovera device-related TEAE (1)	xx (xx.x)	-
At least one opioid use related TEAE (1)	xx (xx.x)	xx (xx.x)
At least one serious TEAE	xx (xx.x)	xx (xx.x)
At least one TEAE leading to study withdrawal	xx (xx.x)	xx (xx.x)

Program Name:

Creation date, time:

Source: Listing 2.1

Note: Percentages are calculated based on the number of subjects in the ITT Population.

(1) Adverse events that are definitely, probably, or possibly related, or for which the relationship is missing, are considered related.

Table 8.2

TREATMENT EMERGENT ADVERSE EVENTS: INCIDENCE BY SYSTEM ORGAN CLASS AND PREFERRED TERM (SUBJECT LEVEL)  
SAFETY POPULATION

System Organ Class/Preferred Term	Iovera (N=xx) n (%)	Standard of Care (N=xx) n (%)
System Organ Class 1	xx (xx.x)	xx (xx.x)
Preferred Term 1	xx (xx.x)	xx (xx.x)
Preferred Term 2	xx (xx.x)	xx (xx.x)
...		
System Organ Class 2	xx (xx.x)	xx (xx.x)
Preferred Term 1	xx (xx.x)	xx (xx.x)
Preferred Term 2	xx (xx.x)	xx (xx.x)
...		

Program Name: Creation date, time  
Source: Listing 2.1  
Note: The denominator for the calculation of the percentage is N, the number of subjects in the treatment group, and the numerator is the number of subjects with at least one AE in that system organ class or with that preferred term.

Table 8.3

TREATMENT EMERGENT ADVERSE EVENTS BY SYSTEM ORGAN CLASS/PREFERRED TERM AND SEVERITY (EVENT LEVEL)  
SAFETY POPULATION

Iovera (N=xx)

System Organ Class/Preferred Term	Mild	Moderate	Severe	Total with Non-Missing Severity	
	n (%)	n (%)	n (%)	n (100%)	n
Any Adverse Event	xx (xx.x)	xx (xx.x)	xx (xx.x)	xx (100.0)	xx
System Organ Class 1	xx (xx.x)	xx (xx.x)	xx (xx.x)	xx (100.0)	xx
Preferred Term 1	xx (xx.x)	xx (xx.x)	xx (xx.x)	xx (100.0)	xx
Preferred Term 2	xx (xx.x)	xx (xx.x)	xx (xx.x)	xx (100.0)	xx
...					

Program Name:

Creation date, time

Source: Listing 2.1

Note: The denominator for the calculation of the percentage is the number of AEs with non-missing severity with the given preferred term or in the given system organ class.

[Note: This table will be continued for Standard of Care.]

Table 9.1

IOVERA PROCEDURE RELATED TREATMENT EMERGENT ADVERSE EVENTS: INCIDENCE BY SYSTEM ORGAN CLASS AND PREFERRED TERM (SUBJECT LEVEL)  
SAFETY POPULATION

System Organ Class/Preferred Term	Iovera (N=xx) n (%)
System Organ Class 1	xx (xx.x)
Preferred Term 1	xx (xx.x)
Preferred Term 2	xx (xx.x)
...	
System Organ Class 2	xx (xx.x)
Preferred Term 1	xx (xx.x)
Preferred Term 2	xx (xx.x)
...	

Program Name:

Creation date, time

Source: Listing 2.1

Note: The denominator for the calculation of the percentage is N, the number of subjects in the treatment group, and the numerator is the number of subjects with at least one AE in that system organ class or with that preferred term. Adverse events that are definitely, probably, or possibly related, or for which the relationship is missing, are considered related.

Table 9.2

IOVERA PROCEDURE RELATED TREATMENT EMERGENT ADVERSE EVENTS BY SYSTEM ORGAN CLASS/PREFERRED TERM AND SEVERITY (EVENT LEVEL)  
SAFETY POPULATION

Iovera (N=xx)

System Organ Class/Preferred Term	Mild	Moderate	Severe	Total with Non-Missing Severity	
	n (%)	n (%)	n (%)	n (100%)	n
Any Adverse Event	xx (xx.x)	xx (xx.x)	xx (xx.x)	xx (100.0)	xx
System Organ Class 1	xx (xx.x)	xx (xx.x)	xx (xx.x)	xx (100.0)	xx
Preferred Term 1	xx (xx.x)	xx (xx.x)	xx (xx.x)	xx (100.0)	xx
Preferred Term 2	xx (xx.x)	xx (xx.x)	xx (xx.x)	xx (100.0)	xx
...					

Program Name:

Creation date, time

Source: Listing 2.1

Note: The denominator for the calculation of the percentage is the number of AEs with non-missing severity with the given preferred term or in the given system organ class. Adverse events that are definitely, probably, or possibly related, or for which the relationship is missing, are considered related.

Table 9.3

IOVERA DEVICE RELATED TREATMENT EMERGENT ADVERSE EVENTS: INCIDENCE BY SYSTEM ORGAN CLASS AND PREFERRED TERM (SUBJECT LEVEL)  
SAFETY POPULATION

System Organ Class/Preferred Term	Iovera (N=xx) n (%)
System Organ Class 1	xx (xx.x)
Preferred Term 1	xx (xx.x)
Preferred Term 2	xx (xx.x)
...	
System Organ Class 2	xx (xx.x)
Preferred Term 1	xx (xx.x)
Preferred Term 2	xx (xx.x)
...	

Program Name:

Creation date, time

Source: Listing 2.1

Note: The denominator for the calculation of the percentage is N, the number of subjects in the treatment group, and the numerator is the number of subjects with at least one AE in that system organ class or with that preferred term. Adverse events that are definitely, probably, or possibly related, or for which the relationship is missing, are considered related.

Table 9.4

IOVERA DEVICE RELATED TREATMENT EMERGENT ADVERSE EVENTS BY SYSTEM ORGAN CLASS/PREFERRED TERM AND SEVERITY (EVENT LEVEL)  
SAFETY POPULATION

Iovera (N=xx)

System Organ Class/Preferred Term	Mild	Moderate	Severe	Total with Non-Missing Severity	
	n (%)	n (%)	n (%)	n (100%)	n
Any Adverse Event	xx (xx.x)	xx (xx.x)	xx (xx.x)	xx (100.0)	xx
System Organ Class 1	xx (xx.x)	xx (xx.x)	xx (xx.x)	xx (100.0)	xx
Preferred Term 1	xx (xx.x)	xx (xx.x)	xx (xx.x)	xx (100.0)	xx
Preferred Term 2	xx (xx.x)	xx (xx.x)	xx (xx.x)	xx (100.0)	xx
...					

Program Name:

Creation date, time

Source: Listing 2.1

